3.4 Safety

Safety and tolerability will be assessed in terms of AEs (including serious AEs [SAEs]), deaths, laboratory data, vital signs, ECGs, physical examination, CCI and exposure. These will be collected for all patients.

3.4.1 Adverse events

Adverse events and SAEs will be collected throughout the study, from informed consent until 30 days after the last dose of olaparib/placebo. Any untoward event occurring subsequent to the 30-day follow-up AE reporting period that the investigator assesses as possibly related to the study treatment should also be reported as an AE.

Adverse Event of special interest

Some AEs that follow clinical concepts are considered as adverse events of special interest (AESIs). They are grouped into the following three categories: Myelodysplastic syndrome / acute myeloid leukemia (MDS/AML), new primary malignancies and pneumonitis. An AstraZeneca medically qualified expert after consultation with the Global Patient Safety Physician will confirm the list of AEs of special interest (group terms and the specific preferred terms) and provide them for analysis. They will be confirmed at the BDRM prior to the final analysis for PFS and at the DRM prior to the final analysis of OS and PFS2.

3.4.2 Treatment exposure

Exposure will be defined as follows:

Total (or intended) exposure of olaparib/placebo:

- Total (or intended) exposure in days = last dose date - first dose date + 1

Actual exposure of olaparib/placebo:

- Actual exposure = intended exposure – total duration of dose interruptions, where intended exposure will be calculated as above. Dose interruptions are any periods when the patient does not take any treatment.

To calculate actual exposure, dose interruptions will include those where a patient forgot to take a dose.

Number of days on 300 mg olaparib/placebo bis in die (bid)

- Number of days on 300 mg olaparib/placebo bid = actual exposure for the dose assigned. Any days with changes in doses will not be counted.

Mean total daily dose per time period

- Sum of the total dose actually received in the time period of interest (considering interruptions and dose reductions) divided by number of days patient on dose for that time period (including interruptions and reductions).

Compliance will be assessed by calculating the actual exposure in days (total planned days - days of interruption) divided by the total exposure in days (last dose date - first dose date + 1) in percent. In addition, patient's individual drug accountability will be listed.

3.4.3 Dose intensity

Relative dose intensity (RDI) is the percentage of the actual dose intensity delivered relative to the intended dose intensity through to treatment discontinuation. Percentage intended dose (PID) is the percentage of the actual dose delivered relative to the intended dose through to progression. Both will be derived using study treatment data up to the date of objective disease progression as defined by RECIST using the investigator site assessments. If the investigator considered that it was in the patient's best interest to continue study treatment past this time, this will not be included in the derivation of dose intensity.

RDI and PID will be defined as follows:

- $RDI = 100\% * d/D$, where d is the actual cumulative dose delivered up to the earlier of progression (or a censoring event) or the actual last day of dosing and D is the

[figure not shown]
intended (or planned) cumulative dose up to the earlier of progression (or a censoring event) or the actual last day of dosing.

- $PID = 100\% * d/D$, where d is the actual cumulative dose delivered up to progression (or a censoring event) and D is the intended (or planned) cumulative dose up to progression (or a censoring event). D is the total dose that would be delivered, if there were no modification to dose or schedule.

For olaparib administered daily for the first two weeks of the cycle, the intended cumulative dose, D, will include all doses received up to midnight on the day of the last non-zero dose.

Figure 1 provides examples of how dose intensity is calculated for olaparib.

Figure 1 Example of dose intensity calculations for olaparib

In this example, patients 1-4 progressed or were censored on Day 15. All four patients received less treatment than intended due to:

- Missed/forgotten doses (Patient 1)
- Dose reduction and early stopping (Patient 2)
- Dose interruption (Patient 3)
- Progression whilst on dose interruption (Patient 4)
- Early stopping (Patient 5)

CCI [REDACTED]

[REDACTED]

[REDACTED]

[REDACTED]

CCI

3.4.4 Laboratory data

Laboratory data will be collected throughout the study, from screening to 30-day follow-up visit as described in [Appendix C](#). Blood and urine samples for determination of pregnancy, haematology, clinical chemistry, and urinalysis will be collected as described in Section 5.2.1 of the CSP. For derivation of post baseline visit values considering visit window and how to handle multiple records, derivation rules as described in Section 3.4.9 below will be used.

3.4.5 Electrocardiograms

Electrocardiogram data will be collected during screening within 7 days prior to starting study treatment and when clinically indicated afterwards. For derivation of post baseline visit values considering visit window and how to handle multiple records present in any visit window, derivation rules as described in Section 3.4.9 below will be used.

3.4.6 Vital signs

Vital signs data including body temperature, height, weight, pulse and blood pressure will be collected as described in [Appendix C](#). For derivation of post baseline visit values considering visit window and how to handle multiple records, derivation rules as described in Section 3.4.9 below will be used.

3.4.7 Physical examination

Physical examination data including the following: general appearance, respiratory, cardiovascular, abdomen, skin, head and neck (including ears, eyes, nose and throat), lymph nodes, thyroid, abdomen, musculo-skeletal (including spine and extremities), and neurological systems will be collected as described in [Appendix C](#).

CCI

3.4.9 General consideration for safety assessments

Time windows

Time windows will need defining for any presentations that summarise safety values by visit (ie. vital signs [incl weight and height], ECG, laboratory, and CCI). The following conventions should also apply:

- The time windows should be exhaustive so that data recorded at any time point has the potential to be summarised. Inclusion within the time window should be based on the actual date and not the intended date of the visit.
- All unscheduled visit data should have the potential to be included in the summaries.
- The window for the visits following baseline will be constructed in such a way that the upper limit of the interval falls half way between the two visits (the lower limit of the first post-baseline visit will be Day 2, ie. the day after the first dose of study drug). The visits Screening, Cycle 1 Day 1, Treatment Discontinuation, 30-Day Follow-up and Survival Follow-up visits will be excluded from remapping. The equation to be used to calculate the time windows for each post-baseline visit is:

Lower limit of interval=Upper limit of previous visit's time window +1

Upper limit of interval=Nominal day at visit + ((nominal day at visit_{i+1} - nominal day at visit_i)/2), where i = 3, 4, 5, 5.1, 5.2..., etc.

If an even number of days exists between two consecutive visits then the upper limit will be taken as the midpoint value minus 1 day.

For example, the visit windows for vital signs data with 28 days between scheduled assessments are:

- Day 29, visit window 2 – 42
- Day 57, visit window 43 – 70
- Day 85, visit window 71 – 98
- Day 113, visit window 99 – 126
- ...
- For summaries showing the maximum or minimum values, the maximum/minimum value recorded on treatment will be used (regardless of where it falls in an interval).
- Listings should display all values contributing to a time point for a patient.
- For visit-based summaries:
 - If there is more than one value per patient within a time window, then the closest value should be summarised, or the earlier in the event the values are equidistant from the nominal visit date. The listings should highlight the value for that patient that went into the summary table, wherever feasible.

- To prevent very large tables or plots being produced that contain many cells with meaningless data, for each treatment group visit data should only be summarised if the number of observations is greater than the minimum of 20 and $> 1/3$ of patients dosed. For example, if 150 patients were dosed in the study ($1/3 * 150 = 50$), data at a particular visit would be summarised if the number of observations is greater than min (20, 50). This would be in each treatment group. Eg, if olaparib arm at Visit 6 has > 20 observations and placebo arm has < 20 observations, the visit data will be summarised for the olaparib arm but not the placebo arm. If both had < 20 patients, the data for that visit will be presented as ‘NC’ (Not Calculated). (This does not apply to PRO data.)
- For summaries at a patient level, all values should be included, regardless of whether they appear in a corresponding visit based summary, when deriving a patient level statistic such as a maximum.
- Baseline will be defined as the last non-missing measurement prior to dosing with study treatment (olaparib or placebo). Any assessments made on day 1 will be considered pre-dose. If an assessment on day 1 is identified as baseline, then it will not be considered as “on treatment”. Where safety data are summarised over time, study day will be calculated in relation to date of first treatment (olaparib or placebo).

Imputation of missing safety data

Missing safety data will generally not be imputed. However, safety assessment values of the form of “ $< x$ ” (ie, below the lower limit of quantification) or “ $> x$ ” (ie, above the upper limit of quantification) will be imputed as “ x ” in the calculation of summary statistics but displayed as “ $< x$ ” or “ $> x$ ” in the listings.

Imputation of missing age

- Age at randomisation: Age at randomisation (baseline) will be calculated from the date of birth. Due to country specific regulations the full date of birth will not be available for all patients. In this case the “age as collected” from the demographics CRF will be used instead.
- Age calculation after randomisation: In order to identify reference ranges for laboratory parameters during the study, the age of a patient needs to be calculated at the timepoint of the collection of the sample. If the date of birth of a patient is only partially collected, then the following rule will be applied: (a) if only day is missing, then calculate age using the first day of the month; (b) if day and month are missing, then calculate age using the first of July. Then use the maximum of this calculated age and of the age as collected at screening for identification of reference ranges. If the date of birth is completely missing, then age as collected will be used.

Imputation of missing dates

For **AEs**, imputation methods will be used on completely missing start dates. Missing AE stop dates are not imputed. Imputation for partial dates is not applicable because partial adverse event dates are not collected in this study. Imputed start dates are used to decide if an observation is treatment emergent and for calculation of the AE event rates. Data listings will show actual date values. Missing AE start dates will be imputed with the first dose date unless the end date indicates it started prior to first dose date, in which case impute the 1st January of the year where the AE stopped as the start date.

For **concomitant medications**, start and stop dates are captured on the CRF with no partial dates being entered in the CRF. If the drug started prior to study start, then this is indicated by a flag “Yes” and the start date is missing. If the treatment with the medication continues, then this is indicated by a flag “Yes” and the stop date is missing. For the analysis of medications, it is required to decide if the medication was taken during the time of study treatment. Such a medication may have started before, on or after the first dose of study drug and was taken in the time frame up to and including 30 days following the last dose of study drug. For patients on study treatment at the time of the PFS analysis, the DCO date will be used as the last dose of study drug.

Therefore, medications are considered as treatment emergent (taken during study treatment) if they:

- started on or before first dose and (stopped on or after first dose or are ongoing) OR
- started after first dose but prior to or on date of last dose plus 30 days.

The following conservative imputation rules will be applied:

- Start and stop date of medication present: apply the rules above
- Start date present but no stop date of medication: assume that medication is ongoing and apply the rules above.
- Start date missing and stop date is not missing and “treatment prior to study start” is “Yes”: Temporarily set start date to the earliest of (date of first dose of study drug, stop date of medication) and apply the rules above
- Start date missing and stop date is missing and “treatment prior to study start” is “Yes”: Temporarily set start date to the date of first dose of study drug, assume the medication is ongoing and apply the rules above
- Start date missing and stop date is not missing and “treatment prior to study start” is missing: Temporarily set start date to the earliest of (date of first dose of study drug, stop date of medication) and apply the rules above
- Start date missing and stop date is missing and “treatment prior to study start” is missing: Temporarily set start date to the date of first dose of study drug, assume the medication is ongoing and apply the rules above

3.5 Resource Use

Resource use outcome variables include the following:

- Total number of hospitalisations
- Length of hospital stay
- Reasons for hospitalisation
- Total number of ICU admissions
- Length of any time spent in an intensive care unit (ICU)
- Reasons for ICU admission

The length of hospital stay will be calculated as the difference between the date of hospital discharge (or death date when occurred during hospital stay) and the start date of hospitalisation (length of hospital stay = end date of hospitalisation – start date of hospitalisation + 1). If the start of study drug is after the start of hospitalisation, then the start of study drug will be used instead (length of hospital stay = end date of hospitalisation – start date of study drug + 1). If a patient was never treated with study drug and the date of randomisation is after the start date of hospitalisation, then the date of randomisation will be used instead (length of hospital stay = end date of hospitalisation – date of randomisation + 1). For patients without an end date at the time of the PFS analysis, the date of death will be used if available; otherwise the DCO date will be used.

Sum of total duration of hospital stay will be considered for analysis if patient was admitted to hospital more than one time during study period.

Hospital and ICU admissions will be counted as a single event if a patient is re-admitted on the same day.

The length of ICU stay will be calculated using the same method as detailed above for the length of hospital stay. However, if the end date of the ICU stay is not available, but the end date of the corresponding hospitalisation period is given, then the end of the ICU stay will be imputed using this date, instead of using the DCO date.

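### The length-of-stay rule in SAP 3.5 never checks the discharge date, so a recorded stay that ended before first dose gets a zero or negative length

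*SAP*

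**What the plan says.** Section 3.5 of the SAP lists the number, length and reasons of hospitalisations and of ICU admissions as resource-use variables. The basic definition is "length of hospital stay = end date of hospitalisation – start date of hospitalisation + 1".

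Two replacement rules follow. For treated patients: "If the start of study drug is after the start of hospitalisation, then the start of study drug will be used instead", with the formula "length of hospital stay = end date of hospitalisation – start date of study drug + 1". For patients who never took study drug and whose randomisation came after the admission: "length of hospital stay = end date of hospitalisation – date of randomisation + 1". Both rules compare the replacement date with the admission date only.

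On repeat admissions the section says: "Sum of total duration of hospital stay will be considered for analysis if patient was admitted to hospital more than one time during study period". It does not define the study period. On intensive care: "The length of ICU stay will be calculated using the same method as detailed above for the length of hospital stay", with a separate provision only for a missing ICU end date. On counting, it says only that a re-admission on the same day is not a new event.

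**The concern.** The replacement is meant to drop the days before treatment from a stay that was still running at first dose. It does this correctly only if discharge was on or after first dose. For a stay that was already over, the start is moved past the end, and the formula returns a value that cannot be a length of stay. Section 3.5 sets no floor at zero and does not exclude such stays.

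The value does not stay isolated, because lengths are added up within a patient. A negative length is then subtracted from days genuinely spent in hospital or in the ICU after first dose. At stake are the hospital-day and ICU-day summaries, not an efficacy or safety conclusion.

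**Working it through.** The SAP states no length-of-stay figure, so there is none to reproduce. The check applies the written rule. All dates below are illustrative.

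**Inputs (all from 3.5).** A = admission, E = end of stay, F = first dose (or randomisation, in never-treated patients). Length = E - A + 1; if F is after A, length = E - F + 1.

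**General result.** If the stay ended k days before F, then E = F - k and the length is (F - k) - F + 1 = 1 - k.

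| Discharge, days before first dose (k) | Length under the rule (1 - k) |
|---|---|
| 0 (day of first dose) | 1 |
| 1 | 0 |
| 2 | -1 |
| 7 | -6 |
| 14 | -13 |
| 28 | -27 |

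**Stay spanning first dose.** Admitted 3 days before and discharged 4 days after: 4 - 0 + 1 = 5 days. The rule works as intended.

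**Stay over before first dose.** In hospital 1 to 5 March (5 days), first dose 15 March: 5 - 15 + 1 = -9. With a later 6-day stay, the patient's sum is -9 + 6 = -3. If the earlier stay is left out, the sum is 6.

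**ICU.** The same method is applied to ICU dates, so an ICU episode can go wrong inside a hospital stay that is handled correctly. Suppose the patient leaves the ICU 3 days before first dose and leaves hospital 2 days after it. The hospital length is 2 - 0 + 1 = 3, but the ICU length is 1 - 3 = -2.

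**Comparison with other rules in the SAP.** Under section 3.4.9, a concomitant medication begun on or before first dose counts as taken during treatment only if it was ongoing or stopped on or after first dose. Section 4.2.13 keeps adverse events from before treatment out of the summary tables. Section 3.5 has no equivalent condition.

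**Can such stays occur?** The rule itself anticipates admissions before first dose. Appendix C has screening from day -28. For safety events, "Adverse events and SAEs will be collected throughout the study, from informed consent until 30 days after the last dose of olaparib/placebo" (section 3.4.1), so observation for adverse events begins before treatment. None of this shows the window for the hospitalisation data themselves.

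**The case against.** The strongest reply is that the triggering data are not shown to exist. The collection window for hospitalisations is not visible. The sentence on adverse events concerns a different data source. Several schedule rows and most of section 4.2.12 are redacted, so collection from Day 1, or an exclusion stated elsewhere, cannot be ruled out. If only stays in progress at first dose were recorded, the hospital formula would be correct. This stands: the effect has to be stated conditionally. It does not repair the rule, which returns impossible values for inputs that 3.5 does not exclude.

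It can also be said that the purpose is plainly truncation and that a negative length would be noticed in output checks. Both are fair, and nothing suggests that the plan intends to subtract days. But a programmer who noticed would have to choose between dropping the stay, setting it to zero and restoring its full length, and these choices do not all give the same summaries. The SAP should make that choice.

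Three stronger readings are tempting but unsupported:

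- A reader might infer that hospital and ICU days are understated by some percentage. That needs the frequency of such stays, the gap to first dose and the total days in hospital, none of which the SAP text gives.
- A reader might infer that the number of admissions is overstated. Section 3.5 gives no counting window, so whether these stays are counted is open.
- A reader might infer a bias between arms. Stays that ended before treatment began should be similar between randomised arms in expectation, and no direction is shown.

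**Conclusion.** The point holds as a defect in a stated formula: for a recorded hospital or ICU stay that ended k days before first dose, or before randomisation in a never-treated patient, the length is 1 - k. A discharge one day earlier gives zero and takes nothing from other stays. From two days on the value is negative, and it reduces the patient's sum only if there is another stay; with a single stay the patient's own length is simply wrong.

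The conclusion assumes that such stays are in the dataset and that no redacted text excludes them. On the visible text no overall size can be given. Resource use does not appear among the visible formal analyses in Table 11 and is outside the multiple testing procedure in 4.2.1, which covers PFS and OS, so the reach is limited to the resource-use summaries. This is a minor point, worth correcting because the logic is certain and the correction is cheap.

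**What to change.** Add to section 3.5: the first-dose date (or the randomisation date, for never-treated patients) replaces the start of a stay only if the stay ended on or after that date; stays that ended earlier are excluded from the length of stay. State that for ICU episodes the condition is applied to the ICU dates, not to those of the surrounding hospital stay. State that the numbers of hospital and ICU admissions use the same window, so that counts and durations describe the same stays.

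No calculated length can then fall below 1 day, and stays spanning first dose keep their present value. The cost is a short addition to the SAP wording and one programming condition.

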4. ANALYSIS METHODS

4.1 General Principles

Efficacy data will be summarised and analysed using the FAS on an ITT basis while HRQoL data will be analysed using the PRO analysis set (see Section 2.1) and will compare the

treatment groups on the basis of randomised treatment, regardless of the treatment actually received. In addition, as sensitivity to the main analyses of PFS, PFS2, OS, TDT, TFST and TSST, analyses of these endpoints will be repeated in those patients whose gBRCAm status is confirmed by the Myriad test.

Results of all statistical analysis will be presented using a 95% confidence interval (CI) and 2-sided p-value, unless specified otherwise. Median and corresponding 95% CI of time to event data (PFS, OS, PFS2, TFST, TSST, TDT) will be calculated using a Kaplan-Meier technique.

When assessing safety and tolerability, summaries will be produced based on the safety analysis set and will compare the treatment groups on the basis of treatment actually received. The safety data will be summarised descriptively and will not be formally analysed.

